## 8.0 Statistical Considerations

Study Design

- 8.1 This is a phase II study in which brentuximab will be initiated after transplant (approximately day 35-60) post engraftment and restaging at day 30 (+10 days) and continued every 21 days for 6 cycles. Dose initiation will be at 1.2 mg/kg for 2 cycles and escalated to 1.8 mg/kg on subsequent 4 cycles. If greater than grade 3 toxicity seen at 1.2 mg/kg dose level then dose will be decreased to 1 mg/kg for all patients at initiation with subsequent cycles at 1.2 mg/kg dose. We will allow intrapatient dose modification based on toxicity.

#### **8.2 Determination of graft failure rate**

Based on literature the standard graft failure rate for reduced intensity transplants is higher than that of myeloablative regimens(23), and in the range of 10%(24). With 20 patients, a two-sided 95% confidence interval for a 5% incidence of graft failure would be 0-14.6%. The primary objective of this study will be to assess the safety of brentuximab as a preventative measure after allogeneic MUD or MRD transplant in high risk CD30+ lymphoma patients. Safety is defined by no more than two secondary graft failures within 6 months of transplant (Day 0), based on an observed graft failure rate of <10% using standard of care treatment. If at any time more than two of these events are observed during the specified time frame, the study will be stopped and no further patients will be accrued.

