## 3.0 Patient Eligibility

### 3.1 Inclusion Criteria:

- 3.1.1 Patients with CD30 positive Hodgkin Lymphoma (HL) or anaplastic large cell lymphoma (ALCL) that have undergone allogeneic or haploidentical SCT in the past 60 days (matched related or matched unrelated donors only).
- 3.1.2 Age 18 to 65 years.
- 3.1.3 Performance status: Zubrod 0-1 or Karnofsky 80-100.
- 3.1.4 Serum creatinine < 1.5 mg/dL or creatinine clearance greater than or equal to 40 cc/min as defined by MDRD method from National Kidney Disease Education Program (NKDEP).
- 3.1.5 Serum direct bilirubin < 1.5 mg/dL (unless Gilbert's syndrome).
- 3.1.6 SGPT < 200 IU/L unless related to patient's malignancy.
- 3.1.7 Evidence of neutrophil and platelet engraftment, defined as platelet count equal or greater than 50,000 mm^3 independent of platelet transfusion or thrombopoietin factor and ANC equal or greater to 1000 without growth factor support for at least 5 days.
- 3.1.8 Patients with previous exposure to brentuximab pre-transplant are eligible for the study.

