## 4.0 Treatment Plan

### 4.1 Treatment Initiation:

Brentuximab will be given as an IV infusion over 30 minutes every 3 weeks for a total of 6 cycles. starting between days 35 and 60 post allogeneic SCT.

Brentuximab dose will be based on actual body weight starting with an initial dose of 1.2 mg/kg for the first 2 cycles and then the dose will be increased to 1.8 mg/kg after the second cycle for all subsequent cycles. Brentuximab dose will be based on actual body weight except for patients weighing more than 100 kg, then dose will be calculated based on 100 kg.

Patients must meet the following criteria to start any cycle of brentuximab:

1. Absolute neutrophil count > 1,000/mm^3 not requiring daily growth factor support on the day of the brentuximab infusion.
2. Platelet count greater than 50,000/mm^3 independent of platelet transfusions or thrombopoietin factor for at least 5 days.
3. No clinical evidence of life-threatening infection.

4. No active bleeding.
5. No uncontrolled acute GVHD (steroid refractory).
6. No CMV re-activation that is dual-refractory to foscarnet and ganciclovir/ No active CMV disease.
7. Creatinine < 1.5 mg/dL or creatinine clearance greater than or equal to 40 cc/min as defined by MDRD method from National Kidney Disease Education Program (NKDEP)
8. Serum bilirubin < 1.5 mg/dL
9. SGPT < 200 IU/L unless related to patient's malignancy

Vital sign monitoring, observation, and treatment of hypersensitivity reactions during and after infusion will be performed per standard of care.

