## 6.0 Study Criteria

### Off Study Criteria:

- 6.1 Patient withdraws consent.
- 6.2 Patient can not tolerate treatment.
- 6.3 Unexpected pattern of toxicity.
- 6.4 Presence of both steroid and 2nd line treatment refractory GvHD while on treatment with brentuximab.
- 6.5 Presence of dual-refractory CMV reactivation to foscarnet and ganciclovir or CMV end-organ disease while on treatment with brentuximab.

- 6.6 Patient's inability of unwillingness to have follow-up visits and/or laboratory tests required by this protocol.
- 6.7 One year after treatment completion.

**Steroid refractory GVHD** is defined as: absence of any response 7 days after the initiation of corticosteroids for skin GVHD or 10-14 days after its initiation for GI and liver GVHD. Patients who are steroid refractory are not eligible to be enrolled on protocol, however if a patient develops GVHD while on protocol, brentuximab will not be held.

**Secondary graft failure** is defined as a sustained declined of ANC  $<0.5 \times 10^9/L$  for 3 consecutive days after initial documented engraftment with no evidence of disease progression and is not associated with concomitant medication that is known to cause cytopenias.

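### The limit of two secondary graft failures in 20 is tied to a general 10% graft failure rate that is not like-for-like with the engrafted patients studied and is probably too high for them

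*Combined protocol and SAP*

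**What the plan says.** Section 1.1 makes the incidence of secondary graft failure the primary objective. Section 8.2 starts from a general figure: "the standard graft failure rate for reduced intensity transplants is higher than that of myeloablative regimens(23), and in the range of 10" percent. It then gives a precision statement: "With 20 patients, a two-sided 95% confidence interval for a 5% incidence of graft failure would be 0-14.6" percent. The safety criterion is at most two secondary graft failures within 6 months of Day 0, "based on an observed graft failure rate of <10% using standard of care treatment". The same count is the stopping boundary: "If at any time more than two of these events are observed during the specified time frame, the study will be stopped".

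Other sections decide who can have an event and what counts as one:

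- Section 3.1.7 requires "Evidence of neutrophil and platelet engraftment, defined as platelet count equal or greater than 50,000" per mm³, together with an ANC of at least 1000, both without support.
- Section 3.2.3 excludes patients whose transplant was itself a treatment for graft failure.
- Section 4.1 has brentuximab "starting between days 35 and 60 post allogeneic SCT".
- Section 6.0 counts a sustained ANC below 0.5 x 10^9/L over 3 consecutive days "after initial documented engraftment with no evidence of disease progression and is not associated with concomitant medication" known to cause cytopenias.

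**The concern.** The benchmark and the endpoint describe different quantities. The 10% is given for graft failure after reduced-intensity transplant; it is not restricted to secondary failure or to patients who have engrafted. In this trial a primary failure cannot occur, because such a patient cannot enter. A patient whose graft fails before enrolment is not enrolled either. Taking 6 months as 180 days, a treated patient is at risk on drug for about 180 - 60 = 120 to 180 - 35 = 145 days of the window that 8.2 counts from Day 0. Falls in ANC with progression or with a cytopenia-causing concomitant drug are not counted.

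The trial has a single arm, so this benchmark is the only comparator for the primary safety conclusion. If the rate expected without brentuximab in such patients is well below 10%, a real increase due to the drug could still be reported as safe. Nothing else in the document bridges the general rate to the studied population, and 8.2 gives no stopping probabilities that would show how the rule behaves.

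**Working it through.** **Inputs.** From 8.2: n = 20, a limit of 2 events, a stop at the 3rd event, a benchmark of about 10%, and a 5% incidence used for the confidence interval. The background rate of secondary failure in engrafted patients is not given. It is treated below as an assumption and shown over a range.

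**Step 1. Reproduce the plan's interval.** Wald: 0.05 ± 1.96 × √(0.05 × 0.95 / 20) = 0.05 ± 0.0955, which is -4.6% to 14.6%. Cutting the lower limit at 0 gives the stated 0-14.6%. The exact (Clopper-Pearson) interval for 1/20 is 0.1% to 24.9%. For 2/20, the highest result still called safe, it is 1.2% to 31.7%.

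**Step 2. Behaviour of the rule.** Over 20 patients, stopping at the third event whenever it occurs has the same overall probability as three or more events in 20. So

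P(declared safe) = P(X ≤ 2) = (1-p)^20 + 20p(1-p)^19 + 190p²(1-p)^18.

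At p = 0.10 this is 0.122 + 0.270 + 0.285 = 0.677.

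| True rate | Declared safe | Stopped |
|---|---|---|
| 2% | 99.3% | 0.7% |
| 3% | 97.9% | 2.1% |
| 5% | 92.5% | 7.5% |
| 10% | 67.7% | 32.3% |
| 15% | 40.5% | 59.5% |
| 20% | 20.6% | 79.4% |

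**Step 3. Relate this to a like-for-like background.** With an assumed background of 2% to 10%, a true 10% is 10/10 = 1 to 10/2 = 5 times background, and a true 15% is 15/10 = 1.5 to 15/2 = 7.5 times. If the background equals the 5% that 8.2 uses for its interval, a doubling to 10% passes 68% of the time and a tripling to 15% passes 40% of the time.

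**Step 4. How far the benchmark could move.** Let s be the unknown share of the 10% that is primary failure. Within one population and one definition, the rate among engrafted patients is (0.10 - 0.10s) / (1 - 0.10s). For s = 50%: 0.05 / 0.95 = 5.3%.

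| Assumed s | Rate if engrafted | Stopped at that rate | Stopped if the drug doubles it |
|---|---|---|---|
| 0 | 10% | 32% | 79% |
| 25% | 7.7% | 20% | 61% |
| 50% | 5.3% | 8.5% | 35% |
| 75% | 2.7% | 1.6% | 9% |

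Removing secondary failures that occur before Day 35 would lower these rates further. The last column is where the choice of benchmark matters: the rule's chance of detecting a doubling falls from 79% to 9% across the range.

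**The case against.** A reader might infer that the background must be below 10% and that the limit is therefore shown to be too lenient. The documents do not support that. The 10% comes from cited sources whose definition, follow-up and split between primary and secondary failure are not reported. A conditional rate is bounded by the overall rate only within one population and one definition, and several features could push the other way:

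- Sections 1.1 and 3.1.1 admit haploidentical transplants, while 8.2 speaks only of matched related and unrelated donors.
- Eligibility does not restrict conditioning intensity; the direction of that effect is unknown.
- The endpoint rests on ANC alone for 3 days, with no chimerism or marrow criterion, and so may be broader than the definition behind the 10%.

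Section 6.0 also leaves open whether brentuximab itself is an excluded concomitant medication. That affects how strict the limit is in practice, not the background rate.

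A reader might also infer that a several-fold excess would usually pass. That depends on the background chosen: at 7.7%, a true 10% is only about 1.3 times background. The pass probabilities of 68% and 40% are properties of two or fewer in 20 and would be the same if 10% were the correct background. Much of the weakness is sample size. With a limit of one event, a true 10% would still pass 39% of the time, and a true 5% would stop the study 26% of the time instead of 7.5%. A tighter count is therefore a trade-off, not a plain correction.

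All of this stands against a claim of proven leniency or of a known size. It does not rescue the 10%: the same uncertainties are further reasons why that figure has not been shown to apply to this cohort.

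**Conclusion.** The point holds in a limited form. The mismatch between a general graft failure rate and secondary failure in already engrafted patients is visible in the document and is not explained. Its likely direction is a benchmark that is too high and a limit that is lenient, and the unreconciled 5% in 8.2 fits that reading, although 8.2 does not call it a background rate. Neither the direction nor the size is established.

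The quantified statement is conditional on binomial sampling in 20 patients and on the assumed 2% to 10% background: a true 10% is called safe about two times in three, and a true 15% about two times in five. Even without settling the background, two events in 20 are compatible with rates up to 31.7%, so meeting the limit cannot by itself show safety relative to 10%. This bears directly on the primary conclusion.

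**What to change.** In Section 8.2:

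1. Keep a stopping rule, but remove the statement that two or fewer events in 20 establishes safety relative to the 10% standard-of-care rate.
2. Report the incidence of secondary graft failure with an exact (Clopper-Pearson) 95% interval, and replace the truncated Wald 0-14.6% with the exact intervals (1/20: 0.1% to 24.9%; 2/20: 1.2% to 31.7%).
3. State the probability that the rule stops the study: 0.7% at a true 2%, 7.5% at 5%, 32% at 10%, 60% at 15% and 79% at 20%.
4. If a rate is available for secondary failure by the Section 6.0 definition, from Day 35-60 to 6 months, in comparable patients engrafted and alive at Day 35-60, use it as the benchmark in place of 10%, ideally by donor type.

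Items 1 to 3 cost a rewritten paragraph. Their downside is a safety conclusion that is less favourable and less definite. Item 4 depends on data not shown to exist: the institution's own series described in Section 2.1 is reported for treatment-related mortality, survival and relapse, not for graft failure. A small series might also be too imprecise to set a count for 20 patients. If it led to a lower count, stopping would become more likely.

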## Protocol Body

### 1.0 Objectives

#### 1.1 Primary Objective:

- 1.1.1 To determine the incidence of secondary graft failure with brentuximab maintenance post allogeneic or haploidentical stem cell transplant.

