#### **8.5 Determination of the response and complete response rates in patients with measurable disease after day +30 restaging and progression free and overall survival of this regimen**

Kaplan-Meier (1958) survival curves will be used to estimate overall survival and progression-free survival. Cox proportional hazards regression analysis may be used to model the association between overall survival and progression-free survival and disease and demographic covariates of interest.

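### The only precision figure for the primary endpoint (0 to 14.6% for a 5% rate in 20 patients) is a truncated Wald interval; the exact interval for 1/20 is 0.1% to 24.9%

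*Combined protocol and SAP*

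**What the plan says.** The primary objective in section 1.1 is one of estimation: "To determine the incidence of secondary graft failure with brentuximab maintenance post allogeneic or haploidentical stem cell transplant". Section 8.2 puts the usual graft failure rate after reduced-intensity transplant at about 10% and then gives the precision expected from this trial: "With 20 patients, a two-sided 95% confidence interval for a 5% incidence of graft failure would be 0-14.6" (per cent). It does not say how that interval was calculated.

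The same section calls the treatment safe if at most two secondary graft failures occur within six months of transplant, and stops accrual if there are more than two. That rule is a count and does not use the interval.

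No other confidence interval or precision figure for graft failure appears in the supplied text (the front pages were not available). The only estimation method named in section 8 is in section 8.5, where Kaplan-Meier "survival curves will be used to estimate overall survival and progression-free survival". No method is named for the primary incidence.

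**The concern.** With 20 patients a 5% incidence is a single event. A large-sample interval for a proportion is unreliable there, and two features of the printed interval point to one having been used. It extends less than 10 points above the estimate, which is narrow for one event in 20. Its lower limit is exactly 0, although a single observed failure already rules out a true rate of zero.

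Since the objective is to determine an incidence, the width of the interval is what a sample of 20 can deliver on it. As written, one failure in 20 appears compatible with true rates up to about 15%, or 1.5 times the 10% reference. If the limit is really 21% to 25%, it is compatible with 2.1 to 2.5 times the reference. On a safety endpoint that overstates how much the trial can rule out. With no method named for the final analysis, the same formula could also be carried into the report.

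**Working it through.** **Inputs, all from section 8.2:** n = 20; incidence 5%, so x = 1; two-sided 95% level (z = 1.96); reference rate about 10%; at most two failures allowed.

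**Step 1: reproduce the stated figure.** The Wald interval is p ± z × √(p(1 − p)/n).

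- √(0.05 × 0.95/20) = √0.002375 = 0.0487
- 1.96 × 0.0487 = 0.0955
- 0.05 ± 0.0955 = −0.0455 to 0.1455, that is −4.6% to 14.6%

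Cutting the negative limit to 0 gives 0 to 14.6%, as printed. Other candidates do not match. Upper limits are 17.1% for Wald with continuity correction, 15.2% using a t quantile, 13.0% for a one-sided 95% Wald limit, and 21.6% for a one-sided 95% exact limit. Agresti-Coull gives 0 to 25.4%.

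**Step 2: intervals suited to one event in 20.**

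| Method | 95% interval for 1/20 | Upper limit minus 14.6 |
|---|---|---|
| Clopper-Pearson: 2.5% quantile of Beta(1, 20), 97.5% quantile of Beta(2, 19) | 0.1% to 24.9% | 10.3 points |
| Wilson (score) | 0.9% to 23.6% | 9.0 points |
| Mid-P | 0.3% to 22.3% | 7.7 points |
| Jeffreys: quantiles of Beta(1.5, 19.5) | 0.5% to 21.1% | 6.5 points |

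**Step 3: direct binomial check.** P(X ≤ 1) = (1 − p)^20 + 20p(1 − p)^19.

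- p = 14.6%: 0.188
- p = 20%: 0.069
- p = 24.9%: 0.025

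A two-sided 95% exact upper limit is the rate at which this probability falls to 2.5%. At 14.6% it is 18.8%, so the data would be far from excluding that rate.

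**Step 4: neighbouring outcomes (exact).**

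- 0/20: upper limit 1 − 0.025^(1/20) = 16.8%. The plan thus claims a tighter bound after one failure than the exact method allows after none.
- 2/20, the most the safety definition allows: 1.2% to 31.7%.

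**Step 5: reading 5% as the true rate.** If 5% is taken as the true rate, the relevant check is coverage at n = 20. The nominal 95% Wald interval covers 5% in 63.9% of trials, the exact interval in 98.4%. Most of the Wald shortfall arises because 0/20, which has probability 0.95^20 = 35.8%, yields an interval of zero width. This reading does not rescue the figure either.

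**The case against.** The best defence is that the arithmetic is right for the formula used, and that the sentence illustrates a hypothetical result and drives no decision. Section 8.2 restates the primary objective as an assessment of safety and defines safety by a count. It sets no precision target, does not say that 20 was chosen to reach this width, and does not commit the final analysis to Wald. All of that is true, and it limits the weight of the point. It does not make 14.6% a usable upper limit, and section 1.1 does make the incidence the thing to be determined.

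A second objection is that Clopper-Pearson is conservative (98.4% coverage at a true 5%) and is the widest of the four intervals tabulated, so the 10-point gap is the largest available. That is fair, and the range of 6.5 to 10.3 points is the better statement of size. The least conservative of the four is still clearly above the printed value.

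A third objection concerns the remedy. If the trial stops at a third failure before 20 patients, the number treated is no longer fixed and a fixed-sample interval is not strictly exact. Patients who die, progress or are lost before six months also need a place in the denominator. Both points stand as caveats for the final report. They do not alter the limits given here for one or two failures in a completed cohort of 20.

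**Conclusion.** The point holds. The stated interval is the Wald interval for 1/20 cut at zero; that identification is inferred from the match, since no method is named. The formula is not valid with one event, and the upper limit is understated by 6.5 points (Jeffreys) to 10.3 points (exact). An honest upper limit for one failure in 20 is about 21% to 25%.

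The consequence is limited to how much uncertainty is disclosed. The count-based safety definition and stopping rule are untouched. The comparison with 10% does not reverse, because 14.6% already exceeds it. The conclusion assumes a completed cohort of 20 patients, each with known six-month graft status. It should be corrected because it is the only precision figure for the primary endpoint and it errs towards reassurance.

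**What to change.** Replace the interval sentence in section 8.2 with wording such as: *If one of 20 patients has secondary graft failure (5%), the exact (Clopper-Pearson) 95% interval is 0.1% to 24.9%; if two do, the most the safety definition permits, it is 1.2% to 31.7%.*

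Then name the analysis method: *The incidence of secondary graft failure will be reported with its exact (Clopper-Pearson) two-sided 95% interval.* It would help to state the denominator there, and to note that the interval treats the number of patients as fixed should accrual stop early. If the sponsor prefers Wilson, mid-P or Jeffreys, naming it and giving its limits is enough.

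The cost is two sentences. No patients or data are added and the stopping rule stays as it is. The only price is a less favourable statement of precision.

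### Section 8.2 makes one count, two or fewer graft failures, both the stopping limit and the definition of safety, but with 20 patients that count cannot support a finding of safe

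*Combined protocol and SAP*

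**What the plan says.** Section 8.2 puts the graft failure rate after reduced-intensity transplants "in the range of 10" per cent. It supports the sample size by precision only: "With 20 patients, a two-sided 95% confidence interval for a 5% incidence of graft failure would be 0-14.6" per cent.

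It then gives one count two jobs.

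- **Verdict:** "Safety is defined by no more than two secondary graft failures within 6 months of transplant (Day 0"), a criterion said to be "based on an observed graft failure rate of <10% using standard of care treatment".
- **Stopping:** "If at any time more than two of these events are observed during the specified time frame", the study closes to accrual.

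The section gives no probability of stopping at any true rate and no rate that would be unacceptable. Its boundary does not depend on how many patients have been treated. Section 1.1 states the primary objective as determining the incidence of secondary graft failure.

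**The concern.** A stopping limit and a final conclusion answer different questions. The first asks whether events have become frequent enough to halt; the second asks what the data say about the true rate. If not reaching a third failure is defined as safety, the trial's main statement rests on a count compatible with rates well above the plan's own reference. A later reader could then take a regimen to have been found safe when the data had not excluded a materially raised graft failure rate. Without the rule's stopping probabilities, neither the sponsor nor the review committee can see how weak or strong a passing result is.

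**Working it through.** **Inputs.** From section 8.2: n = 20; stop at 3 or more events; safe at 2 or fewer; reference rate about 10%; precision statement at 5%. The true rates of 8%, 15% and 20% are assumptions chosen to show a range.

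**The plan's own figure.** Wald interval at 5%: 0.05 ± 1.96 × √(0.05 × 0.95 / 20) = 0.05 ± 0.0955, or −4.6% to 14.6%, cut off at 0. The plan's 0-14.6% reproduces. The Wald method is poor with one event: the exact (Clopper-Pearson) two-sided 95% interval for 1/20 is 0.1% to 24.9%, and the Wilson interval is 0.9% to 23.6%.

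**Crossing probability.** The count can only rise and the boundary is flat, so the chance of ever crossing it over 20 patients equals P(X ≥ 3), with

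P(X ≤ 2) = (1−p)^20 + 20p(1−p)^19 + 190p²(1−p)^18.

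- p = 0.05: 0.3585 + 0.3774 + 0.1887 = 0.9245 (from unrounded terms), so P(stop) = 0.0755.
- p = 0.10: 0.1216 + 0.2702 + 0.2852 = 0.6769 (from unrounded terms), so P(stop) = 0.3231.

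| True rate | Limit crossed | Called safe |
|---|---|---|
| 5% | 7.5% | 92.5% |
| 8% | 21.2% | 78.8% |
| 10% | 32.3% | 67.7% |
| 15% | 59.5% | 40.5% |
| 20% | 79.4% | 20.6% |

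These are chances of crossing the limit. With outcomes known at once, accrual would end before the 20th patient in 29.5% of trials at a true 10%. With six months of follow-up per patient the share would be lower.

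**What a passing count leaves open.** The one-sided 95% exact upper limit is the p at which P(X ≤ x) = 0.05.

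- 0/20: 1 − 0.05^(1/20) = 13.9%.
- 1/20: 21.6%.
- 2/20: 28.3%, with an observed rate of 2/20 = 10.0%.

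Every passing result has an upper limit above 10%.

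**Sample size.** If n were 15, the limit would be crossed in 18.4% of trials at a true 10% and 60.2% at 20%. At n = 25 the figures are 46.3% and 90.2%.

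**Early clusters.** Two failures in the first five patients do not stop accrual. The chance of two or more in five is 8.1% at a true 10% and 26.3% at 20%. As an example, adding a stop at two failures in the first five raises the overall stopping probability by P(exactly 2 in 5) × P(0 in the other 15).

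- At 20%: 0.2048 × 0.0352 = 0.007, from 79.4% to 80.1%.
- At 10%: 0.0729 × 0.2059 = 0.015, from 32.3% to 33.8%. Closure by the fifth patient rises from 0.9% to 8.1%.

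**The case against.** The best defence is that this is a reasonable rule for a small single-arm safety study. It stops 79.4% of the time at a true 20% and only 7.5% at 5%. The wide upper limits come from having 20 patients, not from the rule, and the plan claims no formal test against 10%. All of that stands, and it supports keeping the count as a stopping limit. It does not support calling a passing count safe.

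Four stronger readings are tempting but are not supported.

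- **A reader might infer that the rule closes a harmless regimen in 32% of trials.** That treats 10% as the no-effect rate. Section 8.2 gives 10% as a general graft failure rate for reduced-intensity transplants. The endpoint is secondary failure, and section 3.1.7 admits only patients who have already engrafted. Their background rate may be lower, and the documents give no figure. Over 5% to 10% the range is 7.5% to 32.3%.
- **A reader might infer that the rule passes an unacceptable rate in 21% of trials.** The 20% rate is an illustration; the plan sets no such rate.
- **A reader might infer an arithmetic contradiction, since 2/20 is 10.0% and not under 10%.** The phrase "based on an observed graft failure rate of <10% using standard of care treatment" most naturally describes standard care rather than the trial's threshold. The sentence is ambiguous, not shown to be wrong.
- **A reader might infer that the flat boundary must be replaced.** The two-in-five example barely improves detection at 20% and adds early closures at 10%. Section 8.3 also has a continuous neutropenia trigger that could respond to such a cluster, although it reduces the drug in later patients and does not stop accrual.

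**Conclusion.** The point holds for the verdict of safety, not as a claim that the stopping count is wrong. Following section 8.2 as written, a trial with 2/20 failures would be labelled safe with an exact upper limit of 28.3%, more than twice the plan's 10% reference. A true 15% would earn the label in 40.5% of trials. The crossing probabilities assume 20 treated patients with independent outcomes and a common true rate. The figure of 20 comes from the precision sentence, and the removed front pages may state accrual differently. The upper limits do not depend on which background rate is right. How far the rule over-stops does depend on it, and the documents do not settle that. The flat boundary's failure to react to two very early events is a real property, but changing it is a matter for the sponsor's judgement.

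**What to change.** In section 8.2:

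1. Replace the sentence that defines safety by the count with wording such as: two or fewer secondary graft failures means that the stopping boundary was not crossed; the conclusion rests on the observed rate and its one-sided 95% exact (Clopper-Pearson) upper limit, set against the stated reference rate. This also fits the incidence objective in section 1.1.
2. Print the stopping probabilities for true rates from 5% to 20% beside the rule, as in the table above.
3. State whether the under-10% figure is the standard-of-care benchmark or the trial's own threshold.

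Optionally, the sponsor may consider a boundary that depends on the number treated. Two failures in the first five is only one possibility, and its trade-off should be weighed first.

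The cost is a few sentences, a small table and a less favourable final statement. No extra patients are needed.
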